8.2.4.1.1 Elevation of Liver Function Tests

In clinical studies with AAV-mediated gene transfer, a transient rise in liver aminotransferases and concurrent decline in transgene expression has been observed [Manno 2006; Nathwani 2011a; Nathwani 2014]. This has been hypothesized to be due to the activation of capsid-specific cytotoxic T lymphocytes and destruction of transduced liver cells [Mingozzi 2007]. However, in mice, T-cells activated against AAV capsid were not able to target and eliminate transduced hepatocytes [Wang 2007; Li C 2007; Li H 2007; Siders 2009] unless the transduced hepatocytes co-expressed the wild-type AAV capsid protein [Li C 2007].

The inability to reproduce the observed effects in animal models has made it difficult to assess the validity of the hypothesis or to develop strategies to overcome or minimize aminotransferase elevations. Despite a lack of clear resolution that activation of cytotoxic T lymphocytes leads to a reduction in transgene expression from hepatocytes, appropriate precautions have been incorporated into this study. The use of oral steroids is allowed if a subject experiences elevations in liver aminotransferases.

Liver function tests will be assessed as part of clinical chemistry (Section 8.2.4.1) at the time points specified in the Schedule of Events (Table 15-1 and Table 15-2). Liver function tests will be assessed at a central and local (STAT) laboratory approximately every 4 days through Week 12, which will allow for a rapid detection of any elevations following administration of DTX301. If a subject experiences an increase in liver function tests following treatment with DTX301, the investigator should consider the initiation of steroid treatment as outlined in Section 8.2.4.1.2, and taking into account dosing Cohort (Cohort 1-3). The event should be recorded as an AE or SAE, as defined in Section 9.1.2, on the appropriate pages in the eCRF if it is felt to be clinically significant in the medical and scientific judgment of the investigator.

Cohort 4 (Dosing Process Optimization) will utilize an alternative regimen of corticosteroids, aiming at prophylaxis of AAV-mediated, transient rises in liver aminotransferases as outlined in Section 8.2.4.1.2. The subject must be assessed as clinically and metabolically stable to initiate the prophylactic corticosteroid regimen.

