The most common product-related AE observed in clinical studies with AAV-mediated gene transfer to subjects with moderate to severe hemophilia B has been an asymptomatic transient rise in liver aminotransferases (still within the normal reference range for these laboratory parameters) and concurrent decline in transgene expression approximately 7 to 10 weeks following vector administration [Manno 2006; Nathwani 2011a; Nathwani 2014]. In all cases, the transient rise in liver aminotransferases resolved without clinical sequelae. It has been hypothesized that this vector-induced hepatitis is due to the activation of capsid-specific cytotoxic T lymphocytes and destruction of transduced liver cells [Mingozzi 2007]. As this is the only identified AE with AAV gene transfer and, given that subjects in this study will be closely monitored for vector-induced hepatitis and treated with corticosteroids (Section 8.2.4.1.2), having an interval of more than 14 days between subjects within Cohorts 1 and 2 and 7 days between the first 3 subjects in Cohort 3 does not change either safety evaluations or the medical management of study subjects. To date, no infusion-related or serious AEs (SAEs) have been reported with DTX301. Aligned with previous experience [Manno 2006; Nathwani 2011a; Nathwani 2014], only mild, transient, asymptomatic rises in liver enzymes have been observed in 6 subjects starting approximately 8 days to 7 weeks after vector administration that resolved with an oral corticosteroid taper regimen [Diaz 2019; Ultragenyx Pharmaceutical, data on file;]. To allow for refinement in management of asymptomatic transient rises in liver aminotransferases (vector-induced hepatitis) and concurrent decline in transgene expression following AAV vector administration, Cohort 4 (Dosing Process Optimization) will utilize an alternative regimen of oral corticosteroids. Based on available evidence, it is expected that vector-induced hepatitis will be self-limiting. Therefore, oral prednisone (or prednisolone) will be employed in a prophylactic regimen initiated before dosing with DTX301, sustained for 4 weeks, followed by tapering (Section 8.2.4.1.2). Prophylactic corticosteroid regimens are in use for gene transfer therapies [Audentes 2017 Clinicaltrials.gov identifier: NCT03223194; Abeona Therapeutics 2016 ClinicalTrials.gov identifier: NCT02716246].

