3.2.7 Safety Stopping Criteria

Enrollment will be stopped, and the regulators will be notified if, at any time during the study, any of the following occur:

- Death of a subject following administration of DTX301
- An event with an intensity \geq Grade 3 (according to the Common Terminology Criteria for Adverse Events (CTCAE) [Section 9.1.3]), but excluding hyperammonemic crises (Section 3.2.6), develops following administration of DTX301
- Occurrence of a hepatic malignancy following administration of DTX301

Following DMC review when a stopping rule is met, if the decision is to restart enrollment, a substantial amendment will need to be approved by the regulatory authority.

Protocol: 301OTC01

Abnormal clinically significant laboratory values (clinical chemistry, plasma ammonia, hematology, urinalysis, and coagulation panel) as assessed by the investigator will be considered AEs. Laboratory values that meet any of the above criteria will result in a pause in enrollment until the DMC reviews the data and provide a recommendation for subsequent study conduct.

Any event that meets the above criteria will be reported immediately (within 24 hours) as outlined in Section 9.1.2.2 and the appropriate page(s) in the electronic case report form (eCRF) must be completed. Enrollment and dosing will be temporarily suspended until the situation can be assessed and risks to the subjects mitigated. The DMC will meet on an ad hoc basis if an investigator reports an AE/SAE that meets any of the study stopping criteria to review and assess the event. If study enrollment is suspended, all subjects who have been enrolled will remain in the study and will continue to be monitored through their completion or withdrawal from the study.

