8.2.4 Clinical Laboratory Analyses

Laboratory tests, including LFTs and coagulation panel, will be closely monitored throughout the duration of the study. At any point between scheduled visits, additional, unscheduled assessment for LFTs, plasma ammonia, or any other biomarker to assess subject safety and clinical status may be performed, at the discretion of the investigator.

Investigators will receive flagged notification of any laboratory values that are outside of the normal range. Any abnormal laboratory test results (clinical chemistry, plasma ammonia, hematology, urinalysis, coagulation panel, or other laboratory parameters), including those that worsen from baseline or are felt to be clinically significant in the medical and scientific judgment of the investigator, are to be recorded as AEs or SAEs (Section 9.1.2).

However, any clinically significant safety assessments that are associated with OTC deficiency are **not** to be reported as AEs, **unless** they are judged by the investigator to be more severe than expected for the subject's condition.

Protocol: 301OTC01

All laboratory tests with results that are significantly abnormal during participation in the study should be repeated until the values return to normal or baseline. If such values do not return to normal within a period judged reasonable by the investigator, the etiology should be identified, and the sponsor notified.

Samples of blood, urine, saliva, and stool will be collected for study assessments. Any samples remaining at the end of the study may be stored for up to 15 years and analyzed to better understand the effect of DTX301 on OTC deficiency or other UCDs. The choice to allow retention and future analysis will be optional.

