9.1.1 Definitions

9.1.1.1 Adverse Events

The investigator is responsible for reporting all AEs that are observed or reported during the study, regardless of their relationship to study product or their clinical significance.

Protocol: 301OTC01

An AE is defined as any untoward medical occurrence in a subject enrolled into this study regardless of its causal relationship to study product. Subjects will be instructed to contact the investigator at any time after the subject signs the informed consent if any signs or symptoms develop.

A treatment-emergent AE is defined as any event not present before exposure to study product or any event already present that worsens in either intensity or frequency after exposure to study product.

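### Protocol 8.2.4 and 8.2.4.1.1 give different rules for recording a post-dose liver-test rise as an adverse event, so the primary AE incidence for the main expected toxicity can depend on which section a site follows

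*Protocol*

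**What the plan says.** The primary endpoint is the incidence of AEs, treatment-emergent AEs and serious AEs by dosing cohort, broken down by severity and relationship (Protocol 2 and 10.5.3.1; SAP Table 2-1 and 9.1). Several Protocol passages bear on when a laboratory abnormality becomes an AE.

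- **8.2.4 Clinical Laboratory Analyses.** Any abnormal result, clinical chemistry included, is to be entered as an AE or SAE, "including those that worsen from baseline or are felt to be clinically significant". The one exemption is for findings associated with OTC deficiency that are no worse than expected.
- **8.2.4.1.1 Elevation of Liver Function Tests.** An increase in liver tests after DTX301 is to be entered as an AE or SAE "if it is felt to be clinically significant in the medical and scientific judgment of the investigator".
- **3.2.7 Safety Stopping Criteria, repeated in the synopsis.** "Abnormal clinically significant laboratory values (clinical chemistry, plasma ammonia, hematology, urinalysis, and coagulation panel) as assessed by the investigator will be considered AEs".
- **9.1.1.1 Adverse Events.** The investigator reports all AEs "regardless of their relationship to study product or their clinical significance".

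Section 1.3.1 calls the aminotransferase rise the only identified AE of AAV gene transfer. It says that, with DTX301 so far, "only mild, transient, asymptomatic rises in liver enzymes have been observed in 6 subjects", and that these resolved with an oral steroid taper. Section 8.2.4.1.2 has steroids considered once ALT exceeds ULN and the investigator judges the rise related to DTX301.

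**The concern.** Section 8.2.4 makes abnormality enough for an AE entry. Its subsection 8.2.4.1.1 adds a condition, the investigator's judgment of clinical significance, for the one laboratory event most expected with this product. The two diverge for mild, asymptomatic elevations, which is the pattern the Protocol reports so far.

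What is at stake is ascertainment in the primary AE table. Two sites with the same ALT result could report it differently and both be following the Protocol. The counts of related and Grade 1 events would then reflect recording practice as well as the subjects' experience. Cohorts are so small that a single entry is visible in the percentages.

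**Working it through.** The plan gives no expected AE incidence and no power calculation (SAP 4.9), so there is no planned figure to reproduce. The check is a comparison of the texts, followed by simple arithmetic on cohort size.

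**Step 1. Apply each rule to one case: post-dose ALT just above ULN, no symptoms, judged not clinically significant.**

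| Passage | Result for this case |
|---|---|
| 8.2.4 | AE: the result is abnormal |
| 8.2.4.1.1 | No AE entry called for: the stated condition is not met |
| 3.2.7 and synopsis | Does not call for an entry, but does not forbid one |
| 9.1.1.1 | Silent on laboratory values; applies once something is an AE |

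The direct conflict is between 8.2.4 and 8.2.4.1.1.

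**Step 2. Would a narrower reading of 8.2.4 remove the conflict?** Suppose its *including* clause limits the rule instead of illustrating it. The two limbs are joined by *or*, so worsening from baseline is enough. Exclusion criterion 4 bars ALT or AST above ULN at Screening. A post-dose ALT above ULN in an eligible subject is therefore abnormal and, unless the value had already changed by Day 0, worse than before dosing. It is still an AE under 8.2.4.

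**Step 3. Does other text settle it?**

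- The exemption in 8.2.4 covers findings associated with OTC deficiency, not a vector-induced rise.
- Section 9.1 documents AEs identified from laboratory data where relevant to subject safety, and 9.1.4 says to report when in doubt about a clinical observation. Both lean towards recording, but neither overrides the condition in 8.2.4.1.1.
- Nothing in 8.2.4.1.2 equates starting steroids with clinical significance.
- No sentence ranks one section over another.

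**Step 4. Scope.** Section 8.2.4 speaks of abnormal results. A rise that stays within the reference range, as 1.3.1 describes for the hemophilia B studies, is not clearly an AE under either rule. The conflict is clear only for values above the limit.

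**Step 5. Size.** Inputs: three evaluable subjects in each of Cohorts 1 to 3 for the dose-finding assessment (SAP 3.2.9), and two subjects in Cohort 4 (SAP 3.1). AEs are tabulated by cohort (SAP 3.3 and 9.1). The change in a cohort's incidence of this event from one recording choice is 1/n:

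- n = 3: 1/3 = 33 percentage points
- n = 2: 1/2 = 50 percentage points

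Any expansion of Cohort 3 would raise n and lower the figure for that cohort.

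**The case against.** The strongest reply is that the ALT signal does not depend on AE entries. SAP 9.3 counts subjects with ALT above ULN, and at or above 2.5 times ULN, at each scheduled visit and at the post-baseline maximum. It uses central and local results and takes the higher. It also provides shift tables and ALT plots, and SAP 8.2 plots ALT with steroid dose for each subject. This stands. What it leaves exposed is the AE table: the laboratory count carries no relationship assessment, it is not the primary endpoint, and the SAP describes no reconciliation of it with the AE page.

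A second reply is that a specific section governs a general one, so 8.2.4.1.1 prevails for liver tests. That is a natural reading, but the Protocol does not state it, and a site following the literal words of 8.2.4 would not be wrong.

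A third is that dose finding is hardly touched. A dose-limiting toxicity must be related and Grade 3 or higher, and an investigator would probably judge such an event clinically significant. This also stands.

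Four stronger readings are tempting and are not supported:

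- **That four sections split two against two.** Section 9.1.1.1 does not name laboratory values, and 3.2.7 does not say that other values are not AEs.
- **That the incidence could be reported anywhere from 0/9 to 6/9 (67%).** The 9 is the enrollment figure in the Amendment 5 history and is not given as the denominator for the six subjects. All six rises resolved with a steroid taper, and an investigator who judged a rise vector-related and treated it is unlikely to have called it not clinically significant. Zero is not a realistic lower end.
- **That any comparison of prophylactic with reactive steroids is compromised.** The laboratory displays address that question directly. With two subjects in Cohort 4, an AE-rate contrast would tell little under any recording rule.
- **That every ALT or AST above ULN must be an AE.** That is one possible rule; the documents do not require it throughout.

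**Conclusion.** The point holds as an inconsistency in AE recording that reaches the primary endpoint. Under the current text, a mild post-dose ALT above ULN may or may not enter the AE and treatment-emergent AE incidence, depending on the section a site applies. One such choice is worth 33 percentage points in a cohort of three and 50 in a cohort of two, for this event type.

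Those figures assume the cohort sizes in SAP 3.1 and 3.2.9 and a subject whose only qualifying event is the rise in question. They show sensitivity; they do not estimate how many events went unrecorded. The documents give no count of ALT elevations without an AE entry. Elevations that were not treated with steroids are the most likely to be affected.

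**What to change.** 1. **One rule.** Reconcile Protocol 3.2.7 (with the synopsis), 8.2.4 and 8.2.4.1.1 to a single stated AE-recording rule for laboratory abnormalities, applied alike at all sites and in all cohorts. The sponsor may choose the rule; if it turns on clinical significance, the judgment should be documented for each post-dose ALT above ULN.
2. **Check before lock.** Compare laboratory ALT above ULN (central and local) and corticosteroid starts for ALT rises with the AE page, and query each mismatch.
3. **Display.** Add to SAP 9.1 a listing of any remaining post-dose ALT above ULN without a matching AE, placed beside the primary AE table.

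SAP 3.1 says enrollment in Cohort 4 has concluded, so new Protocol wording alone would change little for subjects already recorded. Steps 2 and 3 carry most of the practical value. The cost is a data-review query on a small number of subjects: about 11 (9 + 2), if the nine enrolled at Amendment 5 and the two in Cohort 4 are all of them. The reported related-AE incidence may rise. No treatment rule changes.

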8.2.4.1.2 Treatment for Possible Vector-Induced Hepatitis

The investigator, in conjunction with the Ultragenyx Pharmaceutical Inc. medical lead will consider starting oral steroid treatment, per protocol, for possible vector-induced hepatitis when a subject's **ALT is greater than the ULN** and is considered by the investigator to be related to treatment with DTX301. The subject must be assessed as clinically and metabolically stable, and intercurrent illnesses (eg, viral infection) or concomitant medications known to affect transaminases, be excluded.

Repeat liver function testing for confirmation of results should be considered to inform the use of steroid treatment. If repeat testing is deemed necessary, every effort should be made to repeat the testing within 24 hours from receipt of test results indicating elevated ALT.

At any point between scheduled visits, additional, unscheduled assessment for LFTs, plasma ammonia, or any other biomarker to assess subject safety and clinical status may be performed, at the discretion of the investigator.

Changes to baseline treatment (ie, ammonia scavenger medications and protein-restricted diet) cannot occur while the subject is treated with corticosteroids or within a 2-week period of completing a corticosteroid taper.

Based on available evidence, it is expected that vector-induced hepatitis will be self-limiting. Therefore, oral prednisone (or prednisolone) will be used per the American Association for the Study of Liver Disease guidelines, with a slight modification in **Cohorts 1 to 3**:

- Week 1: prednisone 60 mg/day
- Week 2: prednisone 40 mg/day
- Week 3 and Week 4: prednisone 30 mg/day
- Week 5 and thereafter: prednisone will be tapered by 5 mg/week until liver enzymes return to baseline levels. The use of prednisone will be recorded on the appropriate page in the eCRF.

Protocol: 301OTC01

Cohort 4 (Dosing Process Optimization) will utilize an alternative regimen of corticosteroids, aiming at prophylaxis of vector-induced hepatitis. Therefore, oral prednisone (or prednisolone) will be initiated before dosing with DTX301, sustained for 4 weeks, followed by tapering as described below. Prophylactic corticosteroid regimens are in use for gene transfer therapies [Audentes 2017 Clinicaltrials.gov identifier: NCT03223194; Abeona Therapeutics 2016 ClinicalTrials.gov identifier: NCT02716246].

- At least 5 days prior to dosing: prednisone 60 mg/day
- Study Day 1 (Week 1) through Week 4: prednisone 60 mg/day
- Study Week 5 through Week 8, tapering every 5 days:

| Taper Dose | Duration |
|----------------------|-----------------|
| 40 mg/ day | 5 days |
| 30 mg/day | 5 days |
| 20 mg/day | 5 days |
| 10 mg/day | 5 days |
| 5 mg/day | 5 days |
| 5 mg every other day | 5 days |

At any time after initiation of prophylactic corticosteroid regimen, additional assessments of plasma ammonia levels, amino acid profiles, or any other biomarker to assess subject safety and clinical status may be performed, at the discretion of the investigator and as clinically indicated.

Utilization of prednisone (or prednisolone) after dosing and after completion of the prophylactic regimen, remains available to all subjects when a subject’s ALT is greater than the ULN and is considered by the investigator to be related to treatment with DTX301. The use of prednisone (or prednisolone) will be recorded on the appropriate page in the eCRF.

8.2.5 Other Laboratory Parameters

Where applicable, details for the preparation and shipment of samples are included in the laboratory manual.

8.2.5.1 Neutralizing Antibodies to Adeno-Associated Virus Serotype 8

Samples for neutralizing antibodies to AAV8 will be collected at the time points specified in the Schedule of Events (Table 15-1) to monitor for a humoral immune response to AAV8. The assay will be performed using a research method (a cell-based assay).

8.2.5.2 Adeno-Associated Virus Serotype 8 Binding Antibody Immunoglobulin G Assay

Samples for the AAV8 binding antibody immunoglobulin G (IgG) assay will be collected at the time points specified in the Schedule of Events (Table 15-1) to monitor for circulating anti-AAV8 antibodies. The assay will be performed using a research method (enzyme-linked immunosorbent assay [ELISA]).

8.2.5.3 Anti-Ornithine Transcarbamylase Antibody Assay

Samples for the anti-OTC antibody assay will be collected at the time points specified in the Schedule of Events (Table 15-1) to monitor for circulating anti-OTC antibodies. The assay will be performed using a research method (ELISA).

8.2.5.4 Viral Shedding

Saliva, urine, and stool will be collected at the time points specified in the Schedules of Events (Table 15-1 and Table 15-2) to monitor for the presence of shed virus. The presence of DTX301 will be determined [REDACTED]. Subjects will be given an appropriate container to collect a stool sample at home. Samples for shedding analysis will be collected until the results are negative on 3 consecutive occasions for each matrix.

8.3 Pharmacokinetics and Pharmacodynamic Assessments

8.3.1 Ureagenesis

The conversion of the stable isotope [1-¹³C]sodium acetate to [¹³C]urea will be determined by gas chromatography mass spectrometry [Tuchman 2008b]. Blood samples will be collected in pre-cooled heparinized tubes before dosing (time 0) and at approximately 0.5, 1, 1.5, 2, 3, and 4 hours (±5 minutes) after [1-¹³C]sodium acetate is administered orally at Screening, Baseline (Day 1), and over time to Week 52 after administration of DTX301 (Table 15-1). [REDACTED]. During Screening, assessment of rate of ureagenesis may be repeated if discrepant with subject's clinical status and severity. Blood samples will be immediately centrifuged to separate the plasma, which will be stored frozen at -70°C until shipped for analysis. Details for the preparation and shipment of samples are included in the ureagenesis manual and the laboratory manual.

8.3.2 Plasma Ammonia Area Under the Curve from Time Zero to 24 Hours

The AUC₀₋₂₄ of plasma ammonia will be determined at Baseline (Day 0) and over time to Week 52 after administration of DTX301 (Table 15-1). Two samples will be collected at time 0 and at approximately 2, 4, 8, 12, 16, 20, and 24 hours (±5 minutes). One sample will be sent to the local laboratory (STAT sample) and 1 sample will be sent to the central laboratory. If possible, ad hoc AUC₀₋₂₄ plasma ammonia should be considered if a subject experiences symptomology deemed by the investigator to meet the definition of an HAC (Section 3.2.6), driven by the underlying disease or at a time of increased metabolic demand, such as intercurrent viral infection, or treatment with corticosteroids, and warranting inpatient monitoring based on investigator discretion.

The subject's plasma ammonia level should be < 100 µmol/L or within the range of historical ammonia levels obtained when the subject was clinically stable (Section 4.1) prior to administering the neuropsychological tests or [1-¹³C]sodium acetate and DTX301 (Day 1 only) (Table 15-1). If the ammonia level is inconsistent with the subject's clinical status, the ammonia level may be repeated to ensure accurate results. If the subject is deemed clinically unstable, the assessments will be held until the subject is determined to be clinically stable. The study site may use the time 0 and time 24 hour plasma ammonia samples to confirm the subject's plasma ammonia. The samples should be sent to the local laboratory (STAT sample) and results available prior to initiating the neuropsychological tests or administering [1-¹³C]sodium acetate and DTX301 (Day 1 only).

Details for the preparation and shipment of samples are included in the laboratory manual.

